## **12.2 Objective Findings**

Clinically significant abnormal objective findings (eg, clinical laboratory value, ECG value, and physical examination observation) will also be recorded as AEs. When a clear diagnosis is available that explains the objective findings, this diagnosis will be recorded as the AE, and not the abnormal objective finding (eg, viral hepatitis will be recorded as the AE, not transaminase elevation). If a definite diagnosis is not available, then record the sign (eg, clinically significant elevation of transaminase levels) or symptom (eg, abdominal pain) as the AE.

Clinical laboratory test results will be reviewed by the Investigator. The Investigator must determine the clinical significance of all out of range values. Clinical laboratory test with possibly drug-related or clinically relevant abnormal values of uncertain causality may be repeated. Any abnormal values that persist should be followed at the discretion of the Investigator. Laboratory reports will be initialed and dated by the Investigator.

All ECG tracings at the study center and ECG over-read reports by the central ECG reader will be reviewed by the Investigator. The Investigator must determine the clinical significance of all abnormal ECGs. An ECG with possibly drug-related or clinically relevant abnormal findings of uncertain causality may be repeated. Any abnormal ECGs that persist should be followed at the discretion of the Investigator. ECG tracings will be initialed and dated by the Investigator.

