#### **15.3.8.2 Analysis visits, baseline, and post-baseline measures**

All data will be organized and analyzed according to the scheduled timing as outlined in Table 3 to 5 Schedule of Assessments (p10~13) and according to the visit denoted in the CRFs. Unscheduled visits may be used if scheduled visits are not available, and details will be prespecified in the statistical analysis plan before the interim analysis is performed. The baseline data for statistical analyses will be defined as the last non-missing data on or before Day 1. In analysis for the open-label treatment phase and the DSP-5423P treatment period, the baseline data of the subjects in the Placebo group will be defined as the last non-missing data before the beginning of DSP-5423P application. Post-baseline data for statistical analysis will be defined as the non-missing data on or after Day 1 and through 7 days after the date of final

application of the study drug (excluding baseline). The data collected at the discontinuation visit will be mapped to the next scheduled visit of the actual discontinuation date.

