6.3 Analysis visits, baseline, and post-baseline measures

All data will be organized and analyzed according to the scheduled timing as outlined in Table 4 to Table 6 Schedule of Assessments and according to the visit denoted in the CRFs. Unscheduled visits may be used if scheduled visits are not available, as specified below. The data collected at the discontinuation visit within 7 days from the final application of study drug will be mapped to the next scheduled visit of the actual discontinuation date, as specified below.

Follow to assign analysis visit;

1. Decide post-base line measures,
2. Assign scheduled visit denoted in the CRFs,
3. Assign CRF discontinuation visits,
4. Assign CRF unscheduled visits, when applicable.

A. Double-blind treatment phase

(i) Baseline analysis visit

Defined as the last non-missing data of CRF Screening or CRF Day 1 (Baseline) visit on or before Day 1. Unscheduled visits will not be used.

Statistical Analysis Plan

Version: 2

Study No. D4904020

(ii) Post-baseline data

Defined as the non-missing data on Day 1 through 7 days after the final application of study drug except for Screening and Day 1 (Baseline) visit. Data assessed on Day 1 and captured in the CRF visits of Week 1, discontinuation, and unscheduled visits will be considered as post-baseline data. Data assessed on Day 1 and captured in the CRF visits of Screening and Day 1 (Baseline) will NOT be considered as post-baseline data.

(iii) Post-baseline analysis visit

The post-baseline data will be mapped to post-baseline analysis visits, ie, Week 1, 2, 4, and 6 as follows:

- (1) CRF Week 1, 2, 4, and 6 will be mapped to the corresponding analysis visits, regardless of the actual day of assessment.
- (2) CRF discontinuation visits will be mapped to the earliest missing analysis visit based on the relative day of assessment as follows:

Assessments and tests	Relative Day	Analysis Visit
PANSS, CGI-S, DIEPSS, C-SSRS, Skin irritation assessment, Body weight, Vital signs	Day 1 to 11	Week 1, 2, 4, 6
	Day 12 to 25	Week 2, 4, 6
	Day 26 to 39	Week 4, 6
	Day 40 or later	Week 6
12-lead ECG, Pharmacokinetic	Day 1 to 11	Week 1, 2, 6
	Day 12 to 25	Week 2, 6
	Day 26 or later	Week 6
Laboratory test	Day 1 to 25	Week 2, 6
	Day 26 or later	Week 6

Note: non-missing analysis visits will not be replaced.

- (3) CRF unscheduled visits will be mapped to the earliest missing analysis visit based on the relative day of assessment as follows:

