7.7.7 Electrocardiograms

ECG parameters (RR interval, QT interval, PR interval, QRS interval, and QTc interval (QTc Fridericia [QTcF] and QTc Bazett [QTcB]) will be listed and summarized by treatment group and visit including LOCF endpoints for the double-blind treatment phase using the safety population and for the DSP-5423P treatment period using the DSP-5423P dosed population. Observed values and change from baseline values will be summarized.

Similarly, interpretation of ECG (normal, abnormal) will be listed and summarized as frequency and percentage by treatment group and visit including LOCF endpoints. Shift from baseline will be summarized as well. Findings of ECG will be listed. If irregular interpretation is obtained, for example “Not evaluable”, it will be set to missing.

QT prolongations are defined in Table 3. For each criterion, subject with abnormal value at least once in the post-baseline (including unscheduled visits) will be identified for the double-blind treatment phase using the safety population and for the DSP-5423P treatment period for the DSP-5423P dosed population. Frequency and percentage of subjects with QT prolongation for each criterion will be summarized by treatment group.

Table 3: QT Prolongation

Parameter	QTc Prolongation
QTcB, QTcF	> 450 msec
QTcB, QTcF	> 480 msec
QTcB, QTcF	> 500 msec
QTcB, QTcF	> 30 msec increased from baseline
QTcB, QTcF	> 60 msec increased from baseline

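### SAP 6.3 bars unscheduled values from the double-blind baseline and counts every unscheduled Day 1 value as post-baseline; this misplaces pre-dose values when Visit 2 is missing or a repeat is dated Day 1

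*SAP*

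**What the plan says.** - **SAP 6.3 A(i), double-blind baseline:** the "last non-missing data of CRF Screening or CRF Day 1 (Baseline) visit on or before Day 1. Unscheduled visits will not be used". B(i)(1) carries this baseline into the DSP-5423P treatment period for the 40 and 80 mg groups.
- **SAP 6.3 A(ii), post-baseline:** "Data assessed on Day 1 and captured in the CRF visits of Week 1, discontinuation, and unscheduled visits will be considered as post-baseline data". There is no check against the time of first application. B(ii)(1) likewise starts post-baseline on On-treatment Day 1 for the 40 and 80 mg groups and excludes only the Screening and Day 1 (Baseline) pages.
- **SAP 6.3 B(i)(2) and B(ii)(2), placebo group on DSP-5423P:** unscheduled values up to and including On-treatment Day 1 may be baseline, and post-baseline starts the next day.
- **Protocol 15.3.8.2:** "The baseline data for statistical analyses will be defined as the last non-missing data on or before Day 1". The record used as baseline is excluded from post-baseline data. On unscheduled visits: "Unscheduled visits may be used if scheduled visits are not available, and details will be prespecified in the statistical analysis plan".
- **Where post-baseline unscheduled values are used:** for QTc, a "subject with abnormal value at least once in the post-baseline (including unscheduled visits) will be identified" (SAP 7.7.7). The markedly abnormal laboratory counts (MAPLV, SAP 7.7.5) work the same way, whatever the baseline value. Double-blind LOCF also uses unscheduled values (SAP 6.4).
- **SAP section 8** declares no change from the planned analyses.

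**The concern.** Values are sometimes repeated before the first patch. Protocol 12.2 foresees this: "An ECG with possibly drug-related or clinically relevant abnormal findings of uncertain causality may be repeated". It says the same of laboratory tests. Repeats therefore tend to fall on subjects with abnormal or unusable readings, who are the ones that matter for the QTc and laboratory tail counts. A rule that refuses a drug-free value as baseline, and then counts it as on-treatment if it is dated Day 1, can misplace it in two ways. The change score may start from an older Screening value, and an abnormality present before treatment may be tabulated as occurring on treatment.

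**Working it through.** The plan gives no figure to reproduce, so the check traces the rules.

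**Windows and timing.** Screening is Day -21 to -4 and Visit 2 is Day -2 to 1 (protocol Table 3). DIEPSS and C-SSRS are first assessed at Visit 2. Antipsychotics in use at screening are to be stopped before washout starts (protocol 10.3.1). For those subjects, a Screening value precedes completed withdrawal.

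**Trace.** The QTc values are hypothetical: Screening 430, Visit 2 470 or missing, unscheduled pre-dose repeat 485, Week 1 440 msec. Two cut-offs from SAP Table 3 are applied: above 480 msec, and an increase above 30 msec. For the protocol rule, the last record up to Day 1 is taken as baseline.

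| Case | SAP baseline | Role of the repeat under the SAP | SAP flags | Protocol baseline | Protocol flags |
|---|---|---|---|---|---|
| A. Visit 2 missing, repeat on Day 1 | 430 (Screening) | post-baseline | >480; increase 485 - 430 = 55 > 30 | 485 | none |
| B. Visit 2 missing, repeat on Day -1 | 430 (Screening) | unused | none | 485 | none |
| C. Visit 2 = 470, repeat on Day 1 | 470 (Visit 2) | post-baseline | >480 only; 485 - 470 = 15 | 485 | none |
| D. Visit 2 = 470, repeat on Day -1 | 470 (Visit 2) | unused | none | 485 | none |
| E. Visit 2 = 470 on Day 1, no repeat | 470 | – | none | 470 | none |

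The fallback to Screening occurs only in A and B, where Visit 2 is missing. The false on-treatment count occurs only in A and C, where the repeat is dated Day 1. Both occur together only in A. In B the Week 1 change is 440 - 430 = +10 under the SAP and 440 - 485 = -45 under the protocol, so baseline choice matters even without a flag.

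**Other routes for a Day 1 unscheduled value.** Under SAP 6.3 A(iii)(3) it fills Week 1 (ECG, rating scales, vital signs, weight) or Week 2 (laboratory) if that visit is empty. Because the earliest qualifying unscheduled value is mapped, it would displace a genuine on-treatment laboratory sample taken as late as Day 25. If nothing later exists, it becomes Week 6 (LOCF). That value feeds the rank ANCOVA of prolactin, glucose and HbA1c (SAP 7.7.5).

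**Within the SAP.** An unscheduled value on the first day of DSP-5423P can be baseline and is never post-baseline for the placebo group. For the 40 and 80 mg groups it is the reverse. Columns of the same DSP-5423P-period tables therefore follow different rules (C-SSRS apart, where SAP 7.7.3 gives the placebo group its double-blind baseline).

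**Size.** The number of pre-dose repeats is not given. As an assumption, if 1% to 5% of the 582 randomised subjects (SAP Appendix II) had one, that is 0.01 × 582 = 6 to 0.05 × 582 = 29 subjects. This is an upper bound for either consequence, since each needs further conditions. With 582 / 3 = 194 per arm, one false case moves an arm's percentage by 1 / 194 = 0.5 points and two by 1.0.

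**The case against.** The case for leaving the rule alone has several parts.

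- **Delegation.** The protocol leaves unscheduled-visit details to the SAP, and the SAP supplies them. This stands as far as it goes. A reader might infer that the SAP reverses the protocol, but the documents support only a narrowing of the general baseline definition in an area left to the SAP.
- **Rarity.** Randomisation follows completion of the Visit 2 assessments, so a randomised subject with no Visit 2 value should be uncommon. Since Visit 2 spans Day -2 to 1, a replacement could also be entered on the Day 1 (Baseline) page. The CRF is not available to settle that. PANSS is hardly exposed, because the Visit 2 score is a randomisation criterion. All this stands and limits the size.
- **No arm favoured.** One rule covers all three arms in the double-blind tables. This stands for those tables. It does not cover the DSP-5423P-period tables: the protocol gives the placebo group a later baseline there but does not call for different treatment of unscheduled values.
- **Conservatism.** For the first application the protocol specifies recording dates only (10.6). ECG times are recorded (11.3.7), but without an application time they do not prove pre-dose status. Treating doubtful Day 1 values as post-baseline keeps true early abnormalities in the tables. This is a good reason for the default when timing is unknown. It is no reason to count a value documented as pre-dose, and false cases in every arm can dilute a real difference.
- **MAPLV makes no claim of emergence.** True: the count disregards baseline, and a persistent abnormality may be counted later anyway. But it is presented as post-baseline, and a pre-dose value is not.

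**Conclusion.** The concern holds in limited form. SAP 6.3 A(i) and B(i)(1) discard a usable pre-dose value when Visit 2 is missing. Separately, A(ii) and B(ii)(1) count an unscheduled Day 1 value as post-baseline even when it is known to precede the first patch. Both differ from the SAP's own placebo rule, and the narrowing from protocol 15.3.8.2 is not declared.

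A reader might infer that any pre-dose retest is replaced by a Screening value and also counted as an on-treatment abnormality. The documents do not support that. A retest normally implies that Visit 2 has a value, which then stays the baseline, and a repeat on Day -2 or -1 is unused. Nor are prolactin, QTc or weight changes generally measured from a value on previous antipsychotics. That needs a subject treated at screening with no Visit 2 value, and the rule is at fault only if an unscheduled pre-dose value also exists.

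The size cannot be computed. The 6 to 29 subjects rest on an assumed frequency of pre-dose repeats and are an upper bound; the true number is probably small. The effect is on safety tail counts and a few change scores, not on the primary comparison.

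**What to change.** 1. In SAP 6.3 A(i) and B(i)(1): where the CRF Day 1 (Baseline) value is missing, use the last unscheduled value dated before Day 1, or dated Day 1 and documented as before the first application, ahead of Screening. A Visit 2 value, where present, stays the baseline.
2. In A(ii) and B(ii)(1): exclude unscheduled Day 1 values documented as pre-dose from post-baseline data. State that Day 1 values of unknown timing remain post-baseline, as now. The opposite default, treating date-only Day 1 values as pre-dose, could remove true post-patch abnormalities.
3. In SAP section 8: record how the rule differs from protocol 15.3.8.2.

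Applied to the trace, with the repeat documented as pre-dose, cases A and B take 485 as baseline, C and D keep 470, and no case is flagged.

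The cost is a few sentences and a small derivation change, made before unblinding, with no new data collection. The remaining weakness is that some Day 1 values of unknown timing stay post-baseline, because the protocol does not specify recording the time of first application.

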Assessment and tests	Relative Day	Analysis Visit
PANSS, CGI-S, DIEPSS, C-SSRS, Skin irritation assessment, Body weight, Vital signs	Day 1 to 11	Week 1
	Day 12 to 25	Week 2
	Day 26 to 39	Week 4
	Day 40 or later	Week 6
12-lead ECG, Pharmacokinetic	Day 1 to 11	Week 1
	Day 12 to 25	Week 2
	Day 26 or later	Week 6
Laboratory test	Day 1 to 25	Week 2
	Day 26 or later	Week 6

If more than one unscheduled visits satisfy the condition, the earliest one

Statistical Analysis Plan

Version: 2

Study No. D4904020

will be mapped to the analysis visit

Note: non-missing analysis visits will not be replaced.

B. DSP-5423P treatment period

(i) On-Treatment Baseline analysis visit

(1) 40 and 80 mg group in the double-blind treatment phase

Same as the Baseline analysis visit for the double-blind treatment phase.

(2) Placebo group in the double-blind treatment phase

Defined as the last non-missing data in the double-blind treatment phase including unscheduled visits assessed on or before the On-treatment Day 1.

(ii) Post-baseline data

(1) 40 and 80 mg group in the double-blind treatment phase

Defined as the non-missing data on 'On-treatment Day 1' through 7 days after the final application of DSP-5423P, except for Screening and Day 1 (Baseline) visit.

(2) Placebo group in the double-blind treatment phase

Defined as the non-missing data on a day after 'On-treatment Day 1' through 7 days after the final application of DSP-5423P.

(iii) Post-baseline analysis visit for the 40 and 80 mg group

The post-baseline data will be mapped to post-baseline analysis visits, ie, On-treatment Week 1, 2, 4, 6, 7, 8, 10, 14, 18, 22, 26, 30, 34, 42, 50, and 58 according to the CRF visits as follows. Unscheduled visits of the open-label treatment phase will not be mapped.

(1) Scheduled visits except for the discontinuation visits will be mapped regardless of the actual day of assessment as follows:

CRF Visits	DB W1	DB W2	DB W4	DB W6
Analysis Visits	OnT W1	OnT W2	OnT W4	OnT W6
CRF Visits	OL W1	OL W2	OL W4	OL W8
Analysis Visits	OnT W7	OnT W8	OnT W10	OnT W14
CRF Visits	OL W12	OL W16	OL W20	OL W24
Analysis Visits	OnT W18	OnT W22	OnT W26	OnT W30
CRF Visits	OL W28	OL W36	OL W44	OL W52
Analysis Visits	OnT W34	OnT W42	OnT W50	OnT W58

DB, double-blind; OL, open-label; OnT, on treatment; W, Week

Statistical Analysis Plan

Version: 2

Study No. D4904020

- (2) Discontinuation visits will be mapped to the earliest missing analysis visit based on the relative day of assessment as follows:

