✧ PANSS, CGI-S, DIEPSS, C-SSRS, Skin irritation assessment,
Body weight, Vital signs

Relative Day	Analysis Visit
Day 1 to 11	OnT W1, 2, 4, 6
Day 12 to 25	OnT W2, 4, 6
Day 26 to 39	OnT W4, 6
Day 40 or later	OnT W6
OL Day 1 to 11	OnT W7, 8, 10, 14, 18, 22, 26, 30, 34, 42, 50, or 58
OL Day 12 to 25	OnT W8, 10, 14, 18, 22, 26, 30, 34, 42, 50, or 58
OL Day 26 to 49	OnT W10, 14, 18, 22, 26, 30, 34, 42, 50, or 58
OL Day 50 to 77	OnT W14, 18, 22, 26, 30, 34, 42, 50, or 58
OL Day 78 to 105	OnT W18, 22, 26, 30, 34, 42, 50, or 58
OL Day 106 to 133	OnT W22, 26, 30, 34, 42, 50, or 58
OL Day 134 to 161	OnT W26, 30, 34, 42, 50, or 58
OL Day 162 to 189	OnT W30, 34, 42, 50, or 58
OL Day 190 to 238	OnT W34, 42, 50, or 58
OL Day 239 to 294	OnT W42, 50, or 58
OL Day 295 to 350	OnT W50 or 58
OL Day 351 or later	OnT W58

Note: non-missing analysis visits will not be replaced.

✧ 12-lead ECG, Pharmacokinetic

Relative Day	Analysis Visit
Day 1 to 11	OnT W1, 2, 6
Day 12 to 25	OnT W2, 6
Day 26 or later	OnT W6
OL Day 1 to 49	OnT W10, 18, 26, 34, 42, 50, or 58
OL Day 50 to 105	OnT W18, 26, 34, 42, 50, or 58
OL Day 106 to 161	OnT W26, 34, 42, 50, or 58
OL Day 162 to 238	OnT W34, 42, 50, or 58
OL Day 239 to 294	OnT W42, 50, or 58
OL Day 295 to 350	OnT W50 or 58
OL Day 351 or later	OnT W58

Note: non-missing analysis visits will not be replaced.

✧ Laboratory test

Relative Day	Analysis Visit
Day 1 to 25	OnT W2, 6
Day 26 or later	OnT W6
OL Day 1 to 49	OnT W10, 18, 26, 34, 42, 50, or 58
OL Day 50 to 105	OnT W18, 26, 34, 42, 50, or 58
OL Day 106 to 161	OnT W26, 34, 42, 50, or 58

Statistical Analysis Plan

Version: 2

Study No. D4904020

OL Day 162 to 238	OnT W34, 42, 50, or 58
OL Day 239 to 294	OnT W42, 50, or 58
OL Day 295 to 350	OnT W50 or 58
OL Day 351 or later	OnT W58

Note: non-missing analysis visits will not be replaced.

- (3) CRF unscheduled visits in the double-blind phase will be mapped to the earliest missing analysis visit based on the relative day of assessment as follows:

Relative Day	Relative Day	Analysis Visit
PANSS, CGI-S, DIEPSS, C-SSRS, Skin irritation assessment, Body weight, Vital signs	Day 1 to 11	OnT W1
	Day 12 to 25	OnT W2
	Day 26 to 39	OnT W4
	Day 40 or later	OnT W6
12-lead ECG, Pharmacokinetic	Day 1 to 11	OnT W1
	Day 12 to 25	OnT W2
	Day 26 or later	OnT W6
Laboratory test	Day 1 to 25	OnT W2
	Day 26 or later	OnT W6

If more than one unscheduled visits satisfy the condition, the earliest one will be mapped to the analysis visit.

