Note: non-missing analysis visits will not be replaced in this step.

- (iv) Post-baseline analysis visit for the placebo group

The post-baseline data will be mapped to post-baseline analysis visits, ie, On Treatment Week 1, 2, 4, 8, 12, 16, 20, 24, 28, 36, 44, and 52 according to the CRF visits as follows. Unscheduled visits of the open-label treatment phase will not be mapped.

- (1) Scheduled visits except for the discontinuation visits will be mapped regardless of the actual day of assessment as follows:

CRF Visits	OL W1	OL W2	OL W4	OL W8
Analysis Visits	OnT W1	OnT W2	OnT W4	OnT W8
CRF Visits	OL W12	OL W16	OL W20	OL W24
Analysis Visits	OnT W12	OnT W16	OnT W20	OnT W24
CRF Visits	OL W28	OL W36	OL W44	OL W52
Analysis Visits	OnT W28	OnT W36	OnT W44	OnT W52

OL, open-label; OnT, on treatment; W, Week

- (2) Discontinuation visits will be mapped to the earliest missing analysis visit based on the relative day of assessment as follows:

Statistical Analysis Plan

Version: 2

Study No. D4904020

- ◇ PANSS, CGI-S, DIEPSS, C-SSRS, Skin irritation assessment,
Body weight, Vital signs

Relative Day	Analysis Visit
OL Day 1 to 11	OnT W1, 2, 4, 8, 12, 16, 20, 24, 28, 36, 44, or 52
OL Day 12 to 25	OnT W2, 4, 8, 12, 16, 20, 24, 28, 36, 44, or 52
OL Day 26 to 49	OnT W4, 8, 12, 16, 20, 24, 28, 36, 44, or 52
OL Day 50 to 77	OnT W8, 12, 16, 20, 24, 28, 36, 44, or 52
OL Day 78 to 105	OnT W12, 16, 20, 24, 28, 36, 44, or 52
OL Day 106 to 133	OnT W16, 20, 24, 28, 36, 44, or 52
OL Day 134 to 161	OnT W20, 24, 28, 36, 44, or 52
OL Day 162 to 189	OnT W24, 28, 36, 44, or 52
OL Day 190 to 238	OnT W28, 36, 44, or 52
OL Day 239 to 294	OnT W36, 44, or 52
OL Day 295 to 350	OnT W44 or 52
OL Day 351 or later	OnT W52

Note: non-missing analysis visits will not be replaced.

- ◇ 12-lead ECG, Laboratory test, Pharmacokinetic

Relative Day	Analysis Visit
OL Day 1 to 49	OnT W4, 12, 20, 28, 36, 44, or 52
OL Day 50 to 105	OnT W12, 20, 28, 36, 44, or 52
OL Day 106 to 161	OnT W 20, 28 36, 44, or 52
OL Day 162 to 238	OnT W28, 36, 44, or 52
OL Day 239 to 294	OnT W36, 44, or 52
OL Day 295 to 350	OnT W44, or 52
OL Day 351 or later	OnT W52

Note: non-missing analysis visits will not be replaced.

C. Open-label treatment phase

For the analysis of open-label treatment phase, analysis visits for all treatment groups are derived using the same algorithm for the placebo group for the DSP-5423P treatment period.

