7 STATISTICAL METHODS

7.1 General Principles

All data processing, summarization and analyses will be performed using the SAS enterprise 5.1 (SAS 9.3) or higher on SAS hosted environment, unless otherwise specified.

Unless otherwise specified, data will be displayed using the following treatment group labels, in the order presented:

- 1) Double-blind treatment phase
 - Placebo group is labelled as PLCB
 - DSP-5423P 40 mg group is labelled as 40MG
 - DSP-5423P 80 mg group is labelled as 80MG
 - Combined group of DSP-5423P 40 mg and 80 mg group is labelled as Active
 - Combined group of DSP-5423P 40 mg, 80 mg and placebo group is labeled as

Statistical Analysis Plan

Version: 2

Study No. D4904020

Overall

Treatment groups for tables and figures

	PLCB	40MG	80MG	Active	Overall
Efficacy	Y	Y	Y		
Safety	Y	Y	Y	Y	
PK		Y	Y		
Others *	Y	Y	Y	Y	Y

* subject disposition, analysis populations, demographics, psychiatric history, prior and concomitant medications, treatment compliance, treatment exposure. Active group will not be displayed for efficacy analyses.

2) Open-label treatment phase and DSP-5423P treatment period

For tables and figures for the open-label treatment phase and DSP-5423P treatment period, subjects are summarized based on the treatment group in the double-blind treatment phase as, PLCB-to-FLEX DOSE, 40MG-to-FLEX-DOSE, 80MG-to-FLEX DSOE, Active-to-FLEX DOSE, and Overall-to-FLEX DOSE. PK analysis for the open-label treatment phase will be based on the latest dose before the PK sampling.

All data collected will be presented in listings by treatment group, subject, visit and date, unless otherwise specified.

Data will be presented in summary tables by treatment group, assessment and visit (where applicable).

Continuous parameters will be summarized using number of subjects (n), mean, standard deviation (SD), median, minimum (min), and maximum (max) values. Mean and median will be displayed to one more decimal place than the original value; min and max will keep the same number of decimal places. SD will be displayed to two more decimal places from the original value. For the case of CGI-S, another decimal point will be added to mean, median, and SD following the rules above. With regard to Pharmacokinetics parameters, Geometric Mean will be displayed to one more decimal place than the original value, and CV% and Geometric CV% will be done to one decimal place. M1/blonanserin will be displayed to three decimal place.

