7.6.2.1.3 DSP-5423P Treatment Period

1. Mean change in PANSS total score from the last evaluation before the initial application of DSP-5423P at each visit
2. Mean change in PANSS subscale scores from the last evaluation before the initial application of DSP-5423P at each visit
3. Mean change in PANSS five-factor model scores from the last evaluation before the initial application of DSP-5423P at each visit
4. Mean change in CGI-S score from the last evaluation before the initial application of DSP-5423P at each visit

Summary statistics for the variables (1) to (4) will be provided in tables and figures by visit and treatment group on the DSP-5423P dosed population. Only (1) and (4) will be repeated by country and race, however figures by race will not be needed.

The estimates of the change in the variables (1) to (4) obtained will be plotted by treatment group and visit with +/-SD

Summaries will be repeated for each PANSS item score in same manner, but Wilcoxon test for change from baseline to LOCF endpoint within each treatment group will be conducted additionally.

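### In the by-visit tables of the DSP-5423P treatment period, most scheduled-visit values in the Overall-to-FLEX DOSE column would come from one group only, because the SAP puts active-first and placebo-first subjects on different week grids

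*SAP*

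**What the plan says.** SAP 6.3 B labels visits in the DSP-5423P treatment period by time since first DSP-5423P application. Subjects randomised to 40 or 80 mg are mapped to "On-treatment Week 1, 2, 4, 6, 7, 8, 10, 14, 18, 22, 26, 30, 34, 42, 50, and 58", and placebo-first subjects to "On Treatment Week 1, 2, 4, 8, 12, 16, 20, 24, 28, 36, 44, and 52". For laboratory tests and ECG the open-label part of the active-first grid is "OnT W10, 18, 26, 34, 42, 50, or 58"; for placebo-first subjects it is "OnT W4, 12, 20, 28, 36, 44, or 52".

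SAP 6.3 B(i) also gives the groups different baselines. Active-first subjects keep the double-blind baseline. Placebo-first subjects use their last double-blind value on or before the first day of DSP-5423P. C-SSRS is an exception: SAP 7.7.3 takes the placebo-first baseline from the double-blind phase.

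For tables and figures of the open-label phase and the DSP-5423P treatment period, SAP 7.1 lists groups by double-blind assignment, ending with "Active-to-FLEX DOSE, and Overall-to-FLEX DOSE". SAP 7.6.2.1.3 says of the PANSS and CGI-S summaries that they "will be provided in tables and figures by visit and treatment group on the DSP-5423P dosed population". Sections 7.7.2, 7.7.3 and 7.7.5 to 7.7.7 also report this period by visit for DIEPSS, C-SSRS, laboratory tests, vital signs and weight, and ECG. Box plots by group and visit are added for laboratory and vital-sign data. No section aligns the two grids or removes the Overall group from by-visit output.

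A common grid exists only in SAP 6.3 C, for the open-label phase, where all groups follow the placebo-group algorithm.

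**The concern.** Each grid is correct for its own group. Open-Week 12, for example, is Week 18 on treatment for an active-first subject and Week 12 for a placebo-first subject. The difficulty arises when a pooled column is printed row by row over both grids. At a week that only one group can reach, the Overall value equals that group's value, yet the label says it covers everyone.

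Long-term safety and efficacy is a secondary objective. A reader following the Overall column for PANSS, prolactin or QTc down the page would see successive rows from different subjects. For change scores the reference points usually differ too: pre-treatment for one group, the end of six weeks on placebo for the other. A step between rows could be taken for a change over time when it is a change of group. The row counts would move as well. With 1:1:1 allocation and similar retention (an assumption), they would switch between roughly two-thirds and one-third of the subjects.

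**Working it through.** The documents state no figure to reproduce. The check compares the visit sets.

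**Inputs**

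- Double-blind weeks for rating scales, skin, weight and vital signs: 1, 2, 4, 6 (SAP Appendix I, Table 4).
- Open-label weeks for the same measures: 1, 2, 4, 8, 12, 16, 20, 24, 28, 36, 44, 52 (SAP 6.3 B and Appendix I).
- Open-label weeks for laboratory tests and ECG: 4, 12, 20, 28, 36, 44, 52.
- Double-blind weeks: 2 and 6 for laboratory tests; 1, 2 and 6 for ECG.

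**Rule**

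- Active-first grid = double-blind weeks, plus (open-label week + 6).
- Placebo-first grid = open-label weeks.

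Applied to the rating scales, this reproduces the 16 and 12 visits printed in SAP 6.3 B.

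**Rating scales, skin, weight, vital signs**

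- Shared: {1, 2, 4, 8} = 4 weeks.
- Union: 16 + 12 − 4 = 24 weeks.
- One group only: 24 − 4 = 20 weeks (83%).
- Active-first only: 6, 7, 10, 14, 18, 22, 26, 30, 34, 42, 50, 58 (12 weeks, of which 10 fall after Week 8).
- Placebo-first only: 12, 16, 20, 24, 28, 36, 44, 52 (8 weeks, all after Week 8).
- After Week 8: 10 + 8 = 18 weeks, none shared.

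**Laboratory tests**

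- Active-first {2, 6, 10, 18, 26, 34, 42, 50, 58}; placebo-first {4, 12, 20, 28, 36, 44, 52}.
- Union 9 + 7 = 16, shared 0.

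**ECG**

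- As for laboratory tests, with Week 1 added to the active-first grid.
- Union 10 + 7 = 17, shared 0.

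**Subsets, rating scales**

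| Data | Weeks in union | Shared | After Week 8 | Shared after Week 8 |
|---|---|---|---|---|
| All | 24 | 4 | 18 | 0 |
| Outside Japan (to Open-Week 28) | 18 | 4 | 12 | 0 |
| Submission analysis (to Visit 108, Open-Week 24) | 16 | 4 | 10 | 0 |

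Discontinuation visits do not change this, because SAP 6.3 B maps them to the subject's own group grid.

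**Common grid of SAP 6.3 C, for comparison:** 12 weeks for the rating scales, with both groups present at 12 of 12.

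**The case against.** The strongest reply is that no by-visit section itself asks for an Overall column. The column comes from the group list in SAP 7.1 read together with sections that say by visit and treatment group, and SAP 7.1 qualifies its by-visit rule: "Data will be presented in summary tables by treatment group, assessment and visit (where applicable"). The protocol asks for these by-visit summaries by treatment group only (15.3.5.3.3, 15.3.6.2, 15.3.6.5). It asks for overall results where no visit grid applies, such as adverse events (15.3.6.1) and antiparkinson use (15.3.6.6). Table shells are not in the documents. This stands as a limit: the column is inferred. It is still the natural reading, since SAP 7.1 applies the group list to tables and figures of this period and no exception follows.

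Second, an attentive reader could detect the problem. Each continuous summary shows n, and the separate columns show which group is empty. That also stands and reduces the harm. It does not make Overall the right label for one group.

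Third, part of the need is already met. SAP 7.6.2.1.1 plans PANSS total by visit in the open-label population as change from the last double-blind value, which gives a common grid and a common reference point. It covers PANSS total only.

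**Conclusion.** The point holds for scheduled-visit Overall values in the DSP-5423P treatment period: 20 of 24 weeks for rating scales, skin, weight and vital signs, 16 of 16 for laboratory tests and 17 of 17 for ECG contain one group only. It rests on reading SAP 7.1 together with the by-visit sections. The affected output is descriptive, and it should be corrected before the tables are produced.

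Several stronger readings are tempting, but the documents do not support them:

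- A reader might infer that no laboratory or ECG table contains a pooled value. The LOCF-endpoint rows required by SAP 7.7.5 and 7.7.7 do pool the groups.
- A reader might infer that the rows strictly alternate after Week 8. For the rating scales, Weeks 30 and 34 are both active-first only.
- A reader might predict a see-saw of a given size in mean PANSS change. The documents give no long-term values for these groups, so no size can be stated.
- A reader might conclude that the long-term objective is undermined as a whole. Adverse event summaries, counts of markedly abnormal values and QTc prolongation at any time, and the separate group columns do not depend on the shared grid. PK is summarised by latest dose. The primary analysis is untouched.

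**What to change.** In SAP 7.1 and 6.3 B, state that Overall-to-FLEX DOSE is omitted from by-visit tables and figures of the DSP-5423P treatment period, with two exceptions: Weeks 1, 2, 4 and 8 for rating scales, skin, weight and vital signs; and the LOCF endpoint for all measures.

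Where a pooled column by visit is wanted, give it on the open-label week grid of SAP 6.3 C. That grid cures the row composition but not the difference in baselines. Either add a footnote that the groups' baselines differ, or report change from the last double-blind value, as SAP 7.6.2.1.1 already plans for PANSS total.

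Pooling adjacent on-treatment weeks (12 with 14, 16 with 18, and so on to 50 with 52) would not be an adequate substitute. On the laboratory and ECG grids, five of the eight pairs (12–14, 16–18, 20–22, 24–26, 28–30) would still hold one group only.

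The cost is fewer pooled by-visit cells and small changes to SAP wording and table shells. No new data are needed, and the protocol's requests for these summaries by treatment group are still met.
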